### 10.2.3 Clinical Examination

- Per RECIST v1.1 and unidimensional irRC, imaging-based evaluation should always be done rather than clinical examination unless the lesion(s) being followed cannot be imaged but can be assessed by clinical exam.
- Clinical lesions will only be considered measurable when they are superficial and  $\geq 10$  mm in diameter as assessed using calipers (eg, skin nodules).

## 10.3 Central Review for Imaging Interpretation

Central radiologic review for evaluation of tumor response will only be conducted for patients who have CR, PR, or SD by internal review at the **24-week** disease assessment time point.

# 11 CORRELATIVE STUDIES

Refer to Section [1.8](#) for a description of the plans for correlative studies using collected blood samples.

## 11.1 Patient Participation

Participation in the correlative studies using blood samples is a study requirement for all patients.

## 11.2 Collection, Processing, and Distribution of Samples

- The study team will coordinate collection and de-identification of all correlative blood samples.
- Questions regarding study requirements should be directed to the study team. The Principal Investigator should be contacted in the event that a correlative sample must be missed or is found to be inadequate.

## 11.3 Blood Sample Collection Time Points

Blood samples will be collected at the following 6 time points:

- Prior to initiation of SRT (after study registration)
- Prior to the 2nd SRT fraction
- After the last SRT fraction (**on the same day**)
- At the following time points after the last SRT fraction:
  - At 8 weeks (+/- 2 weeks)
  - At 24 weeks (+/- 2 weeks)

- At 52 weeks (+/- 4 weeks)

#### **11.4 Instructions for Blood Sample Collection**

At each time point:

- Collect 10 mL of blood in a purple-top tube
- Invert 8-10 times after collection and deliver at ambient temperature within 2 hours following collection to the laboratory of [name] in the Department of Radiation Oncology.

#### **11.5 Blood Sample Labeling**

Each collected blood sample should be labeled as follows:

- Study number
- Patient study identification number
- Date of sample collection
- Time of sample collection
- Study time point

#### **11.6 Testing and Analysis**

Testing and analysis of the blood samples will be performed by [name] and [name] [name].

#### **11.7 Tracking Blood Samples**

Collection and distribution of all blood samples will be logged by the study team in OnCore.

### **12 STUDY CALENDARS**

Required tests, exams, collection of samples for correlative studies, and study treatment are listed on 2 tables: requirements during screening on [Table 4](#) and requirements during treatment and follow-up on [Table 5](#). At the discretion of the treating radiation oncologist, additional SRT-related standard tests and exams may be performed. At the discretion of the treating medical oncologist, additional tests may be performed to continue the standard care the patient was receiving during PD-1 or PD-L1 inhibiting therapy prior to study registration.

**Table 4. Study Calendar – Screening Requirements**

Tests, Exams, and Other Requirements	Prior to Study Registration
Informed Consent	Prior to study-specific procedures
Medical/Surgical History A	Within 28 days
Demographics	
Tumor Imaging B	
Disease Assessment C	
Radiation Oncology Consultation D	
Medical Oncology Consultation E	
Concurrent Medications F	Within 14 days
Baseline Conditions and Symptoms	
Baseline Assessment of prior and ongoing PD-1/PD-L1-related AEs G	
Physical Exam	
Height and Weight	
Vital Signs including BP	
Performance Status ( Appendix 1 )	
CBC with Differential; Platelets	
Serum Chemistry H	
Pregnancy Test I	

A. Assessment of Medical History will include, if known, baseline tumor characteristics: PD-L1 expression and Microsatellite Instability-High (MSI-H) status
 
B. Baseline imaging should be contrast-enhanced and include the following:
 

CT, PET-CT, and/or MRI of all suspected sites of disease within 28 days prior to study registration; for patients with a documented CT and/or MRI contrast allergy, the CT and/or MRI may be performed without contrast.

Brain (CT or MRI) within 1 year prior to study registration to screen for brain metastasis. In patients with known brain metastasis, brain imaging must be performed within 28 days prior to study registration.

 
Note: The imaging used at baseline should be used at each subsequent imaging time point.
 
C. Disease assessment by imaging and/or clinical examination. For patients with brain metastasis receiving SRS, disease assessment includes documentation of neurologic status and dosing history of steroids used for CNS edema management.
 
D. To determine if the patient is a candidate for SRT and if there is at least one lesion that will not receive SRT.
 
E. Consultation or, if the patient's treating medical oncologist is a VCU MCC sub-investigator, documentation that the patient is a candidate to continue PD-1 or PD-L1 inhibiting therapy.
 
F. Refer to Section 6.5.3.
 
G. Assessment to determine if AEs related to previous therapy have resolved or stabilized.
 
H. Chemistry includes the following panels and tests: basic metabolic panel (sodium, potassium, carbonate, chloride, glucose, calcium, BUN, and creatinine); hepatic panel (ALT, AST, ALP, total bilirubin, direct bilirubin, albumin, and total protein).
 
I. Only required for WCBP (see Section 4.1.12); if required, perform within 14 days prior to study registration. If SRT cannot begin within 14 days of a negative pregnancy test, the pregnancy test must be repeated prior to initiation of SRT. Serum or urine qualitative pregnancy test is acceptable.
	

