### 3.3 Primary Endpoint

Proportion of patients with improved disease control (see Section [13.1](#)) per Response Evaluation Criteria in Solid Tumors Version 1.1 (RECIST v1.1) and, if brain metastases are present, per Response Assessment in Neuro-Oncology for Brain Metastases (RANO-BM) criteria at 24 weeks following SRT

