**Table 3. RANO-BM and iRANO Criteria for Brain Metastasis**

Response	RANO-BM Criteria*
Complete Response	Disappearance of all CNS target lesions for $\geq 4$ weeks; disappearance of all enhancing CNS non-target lesions; no new lesions; no steroids; clinically stable or improved
Partial Response	$\geq 30\%$ decrease in sum of longest diameters of target lesions for $\geq 4$ weeks; no new lesions; stable or decreased steroid dose; clinically stable or improved
Stable Disease	Does not qualify for complete response, partial response, or progressive disease
Progressive Disease	$\geq 20\%$ increase in the sum of longest diameters of target lesions; and at least one lesion must increase by an absolute value of 5 mm or more; or unequivocal progression of existing enhancing non-target CNS lesions; or new lesions; or unequivocal progression of existing tumor-related non-enhancing (T2/FLAIR) CNS lesions
*iRANO recommends confirmation of disease progression on follow-up imaging 3 months after initial radiographic progression if there are no new or substantially worsened neurological deficits that are not due to comorbid events or concurrent medications and if the patient's duration on the current immunotherapy regimen is 6 months or less. For this trial, that 6-month window will begin with the initiation of protocol therapy and not that patient's first exposure to immunotherapy. If follow-up imaging confirms disease progression, the date of actual progression should be back-dated to the date of initial radiographic progression. The appearance of new lesions 6 months or less from the initiation of protocol therapy alone does not define progressive disease.	

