### 10.2.2 Imaging

Only imaging of the initial sites of disease is required at subsequent time points to provide tumor measurements for assessment of antitumor effect. The same type of imaging used at baseline should be used at each scheduled assessment.

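### Brain CT is allowed for patients whose primary endpoint uses RANO-BM, but one RANO-BM route to progression (T2/FLAIR lesions) cannot be read on CT

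*Combined protocol and SAP*

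**What the plan says.** **Which brain scan.** Table 4 footnote B describes the brain scan used to look for metastases, due within a year of registration, as "Brain (CT or MRI", so either modality is accepted. For patients already known to have brain metastases it adds: "In patients with known brain metastasis, brain imaging must be performed within 28 days prior to study registration". That sentence sets a date and names neither modality nor sequence. The bullet on suspected disease sites also accepts CT, PET-CT or MRI. Baseline imaging "should be contrast-enhanced", with one exception: "for patients with a documented CT and/or MRI contrast allergy, the CT and/or MRI may be performed without contrast".

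**Which scan afterwards.** The note to footnote B says: "The imaging used at baseline should be used at each subsequent imaging time point". Section 10.2.2 agrees: "The same type of imaging used at baseline should be used at each scheduled assessment". Table 5 footnote J says the same.

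**How the brain is scored.** Section 3.3 defines the primary endpoint by RECIST v1.1 and, when brain metastases are present, "per Response Assessment in Neuro-Oncology for Brain Metastases (RANO-BM) criteria at 24 weeks following SRT". Table 3 lists several alternative RANO-BM routes to progressive disease (PD), the last being "or unequivocal progression of existing tumor-related non-enhancing (T2/FLAIR) CNS lesions". Stable disease (SD) is whatever is not complete response (CR), partial response (PR) or PD.

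**What counts as success.** Under Section 13.1, a patient enrolled with progression succeeds with SD, PR or CR. A patient enrolled with stable or plateaued disease needs PR or CR.

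**The concern.** T2 and FLAIR are MRI sequences. A patient who enters on brain CT and continues on it, as the plan advises, cannot be assessed for one of the listed routes to PD. Because SD is the residual category, progression by that route would be recorded as SD, or as PR if the target lesions have shrunk enough. Among patients enrolled with progression this turns a failure into a success. Patients followed by CT and by MRI are then judged by different working definitions of the primary endpoint.

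The effect falls on the patients with brain metastases. Section 13.2 caps those irradiated in the brain alone because evidence on them is limited, and Section 13.3 analyses that group as a subset. Patients irradiated in both brain and body are not capped.

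**Working it through.** **1. Does another provision close the gap?**
- Section 6.3.6 requires CT-based simulation for radiotherapy planning, so planning does not guarantee an MRI.
- Section 13.5.2 asks for an objective response assessment at 24 weeks, not one that can support every RANO-BM criterion. CT-followed patients are therefore evaluable.
- Section 10.3 sends CR, PR and SD cases at 24 weeks to central review, which cannot read a sequence that was never acquired.
- Table 4 footnote C and Table 5 footnote J require neurologic status and steroid history, but Table 3's PD row has no neurologic or steroid route.
- Section 10.2.1 allows extra assessments at discretion; none has to be MRI.

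Nothing closes it.

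**2. Who can be misclassified?** A false success needs all of the following:
- brain metastases followed by CT;
- T2/FLAIR progression with no other RANO-BM PD route met (target growth, enhancing non-target progression, new lesions);
- no RECIST progression outside the brain;
- either enrolment with progression, or enrolment as stable or plateaued with a PR or CR scored despite the T2/FLAIR progression.

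**3. The plan's own design.** Inputs from Sections 13.2 and 13.3: 10% versus 25%; 14 patients in stage 1, continue with at least 2 successes; 42 in total, positive with at least 8.

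P(go) = sum over x = 2 to 14 of P(X1 = x) × P(X2 ≥ 8 − x), with X1 ~ Bin(14, p), X2 ~ Bin(28, p).

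- p = 0.10: 0.0464, within the stated 5%.
- p = 0.25: 0.804, matching the stated 80%.

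The design reproduces, with 5.00 − 4.64 = 0.36 percentage points of slack.

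**4. Illustrative size.** The documents give neither the number followed by CT (k) nor the share of failures that would be misread, so both are assumptions. Let k of the 42 have apparent success 0.10 + d and the rest 0.10, with 1 of 2, 1 of 3, 2 of 6 or 4 of 12 falling in stage 1. An addition d means that d/0.90 of these patients' true failures are misread: 1.1% for 1 point, 2.2% for 2, 5.6% for 5 and 11.1% for 10.

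| CT-followed patients (k) | d = 1 point | d = 2 points | d = 5 points | d = 10 points |
|---|---|---|---|---|
| 2 | 4.8% | 4.9% | 5.2% | 5.8% |
| 3 | 4.8% | 5.0% | 5.5% | 6.4% |
| 6 | 5.0% | 5.3% | 6.4% | 8.6% |
| 12 | 5.3% | 6.1% | 8.7% | 14.2% |

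Entries are the probability of a positive conclusion when the true rate is 10%. Before rounding, 3 patients at 2 points give 4.97% and 6 patients at 1 point give 4.97%, both just under 5%.

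**The case against.** The strongest reply is that the route to a false success is narrow. Target growth, enhancing non-target progression and new lesions are separate PD routes that do not depend on T2/FLAIR. Section 4.1.6 requires unirradiated measurable disease, outside the brain when brain metastases are treated, and RECIST progression there still makes the patient a failure. This stands, and it is why the smaller additions in the table deserve as much weight as the larger ones.

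Four stronger readings are tempting, and the documents do not support them:

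- *CT is locked in.* All three carry-forward statements say should, and extra assessments are allowed. CT for known brain metastasis is permitted largely because no modality is named, not prescribed for RANO-BM follow-up.
- *Non-contrast imaging is an equal problem.* Contrast is the default and the exception is documented allergy, so this part is minor.
- *Every error favours the treatment.* An unreadable CR can count against it, and for patients enrolled stable or plateaued, a PD read as SD is still a failure.
- *Two CT-followed patients are enough to break the 5% level.* That holds at 5 or 10 added points, not at 1 or 2.

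The effect on the iRANO endpoint (Section 3.4.1) is also weaker, since the Table 3 note recommends confirming early progression on later imaging in defined circumstances. Finally, RANO-BM is adopted by citation, and the cited source may set imaging requirements. That cannot be checked here; the protocol's own imaging rules do not state any such requirement.

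**Conclusion.** The mismatch is real. The imaging the plan permits cannot support one of the criteria it uses to score the primary endpoint, and no other section repairs this. For patients enrolled with progression, the missed PD route biases towards success. For those enrolled stable or plateaued it does so only where a PR or CR is scored despite T2/FLAIR progression. In both groups it matters only when no other RANO-BM route and no extracranial RECIST progression is met.

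The size cannot be established from the documents. It may be negligible if few patients have CT, and material if many do and T2/FLAIR-only progression is not rare. The case for acting rests on having one definition of progression for all patients with brain metastases, not on a particular type I error. Cheap improvement.

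**What to change.** - **Table 4 footnote B:** keep the choice of CT or MRI only for screening patients without known brain metastasis. For patients to be assessed by RANO-BM, specify contrast-enhanced brain MRI including T2/FLAIR at baseline and at each disease assessment unless contraindicated.
- **Section 10.2.2 and Table 5 footnote J:** mirror this requirement.
- **Analysis:** flag patients followed by CT or without contrast as not fully assessable by RANO-BM. Add to Section 13.3 a sensitivity analysis of the primary result that counts them as non-successes.

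The 42 evaluable patients and the decision rule do not change. The cost is MRI for the few who would otherwise have CT, plus one analysis line. Imaging of the initial disease sites is already required at each assessment, so this changes the modality and not the number of assessments; the documents do not say whether MRI fits the existing appointments.

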**Table 5. Study Calendar – On-Study, Study Treatment, and Follow-Up**

Requirements	On Study	During SRT		Follow-Up Post-SRT in Year 1 (Weeks)					Follow-Up in Year 2
		Week 1	Week 2	4 A	8 B	16 B	24 B	52 C	
Weight				X	X		X		
Performance Status ( Appendix 1 )				X	X		X		
Assessment of AEs (Section 8 )		X		X	X	X D	X D	X D	X E
Concurrent Medications F				X			X		
Physical Exam				X	X		X		
CBC with Differential				X	Frequency per Treating Investigator H				
Serum Chemistry G				X					
Pregnancy Test	X I (if required)								
Imaging/Disease Assessment J					X K	X	X L	X M	X N
Collection of Correlative Blood Samples (Section 11 )	X (prior to 1 st SRT fraction)	X (prior to 2 nd SRT fraction)	X (after last SRT fraction on same day)		X		X	X O	
SRT (Section 6.3 )		X (up to 10 fractions over 1-2 weeks) P							
Administration of PD-1 or PD-L1 Inhibitor (Sections 6.2 and 6.4 )	X (prior to 1 st SRT) Q	X (after last SRT fraction on same day)		X Continue According to Prescribing Information Until 12 Months Following Last SRT Fraction					X R
Survival Follow-Up									X S

**Table 5 Footnotes:**

- A. Within +/- 1 week.
- B. Within +/- 2 weeks.
- C. Within +/- 4 weeks.
- D. Assessment and reporting limited to AEs that required discontinuation of the PD-1/PD-L1 inhibitor **and** steroid management.
- E. AEs will continue to be assessed every 2-6 months through end of year 2 in those who continue on PD-1 or PD-L1 inhibitor therapy in accordance with Section [6.7](#).
- F. Refer to Section [6.5.3](#).
- G. Serum chemistry includes the following panels and tests: basic metabolic panel (sodium, potassium, carbonate, chloride, glucose, calcium, BUN, and creatinine); hepatic panel (ALT, AST, ALP, total bilirubin, direct bilirubin, albumin, and total protein).
- H. After week 4, labs are done as part of routine care assessments, and these lab values are not required to be entered in eCRFs. They will be reviewed as part of AE assessments and, as applicable, AE eCRF entry.
- I. For WCBP, the pregnancy test must be repeated if the pre-entry test was performed more than 14 days prior to initiation of SRT. If required, either a urine or serum qualitative pregnancy test may be performed.
- J. The imaging (and/or clinical assessment) used at baseline should be used at each subsequent time point; refer to Section [10.1](#) for information regarding the response criteria to be used. For patients with brain metastasis receiving SRS, disease assessment includes documentation of neurologic status and dosing history of steroids used for CNS edema management.
- K. A goal of imaging at 8 weeks post-SRT is to rule out progressive disease.
- L. Imaging findings at the 24-week time point will be used for analysis of the primary endpoint (Section [13.3](#)). Refer to Section [10.3](#) regarding central review requirements. An optional disease assessment may be done at approximately 28 weeks (at least 4 weeks after the 24-week disease assessment) if needed to confirm response status.
- M. In the absence of post-SRT disease progression, continue with imaging and disease assessment every 2-3 months until 12 months following completion of SRT.
- N. In the absence of post-SRT disease progression, continue with imaging every 2-6 months until 2 years following completion of SRT. (If the patient has initiated a new cancer treatment, imaging is no longer required.)
- O. If the patient is available and willing to have a final blood sample collected for the correlative studies.
- P. SRT must be administered by VCU Radiation Oncology and must begin within 4 weeks following study registration; refer to Section [6.3](#) for additional SRT requirements and instructions.
- Q. If one dose of the PD-1 or PD-L1 inhibitor needs to be given after study registration (before the first SRT fraction), the pre-SRT dose (if given) must be timed so that the next dose is given on the same day as the last SRT fraction.
- R. At the discretion of the treating medical oncologist, the PD-1 or PD-L1 inhibitor may continue to be administered after 52 weeks following completion of SRT if there has not been disease progression following SRT.
- S. For patients with post-SRT disease progression, follow-up can be limited to assessment of vital status until 2 years after completion of SRT.

## 13 STATISTICAL CONSIDERATIONS

### 13.1 Study Design

This is a single-arm phase 2 study of SRT and PD-1 or PD-L1 inhibiting therapy for patients with advanced solid tumors who achieved disease control during PD-1 or PD-L1 inhibiting therapy. The primary objective is to determine if SRT can restore the benefit of PD-1 or PD-L1 inhibiting therapy in patients with an advanced solid tumor who had disease control from PD-1 or PD-L1 inhibiting therapy but did not continue to improve. For patients enrolled with progression, this would mean SD, PR, or CR. For patients enrolled with stable or plateaued disease, restoration of benefit would be an objective response, ie PR or CR.

### 13.2 Sample Size and Accrual Rate

Given that only approximately 10% of patients who continue PD-1 or PD-L1 inhibition after progression or plateau on a prior PD-1 or PD-L1 inhibiting agent experience improved disease control ([18](#), [45](#), [98](#)), we would consider an improved disease control rate of 25% (relative to 10% of patients who do not receive radiotherapy) with the combination of SRT and PD-1 or PD-L1 inhibiting therapy to be promising and worthy of further study. To statistically test whether the disease control improvement rate meets our disease control criteria, the study will require a sample size of 42 evaluable patients to have 80% power at 5% level of significance. We anticipate that 10% of enrolled patients may be inevaluable; therefore, up to 46 patients are required to ensure that sufficient patients will be evaluable. Patients who are not evaluable for efficacy as defined in Section [13.5.2](#) will be replaced.

Given the limited data on the immunogenicity of brain metastases, enrollment of patients who receive SRT to brain metastases alone will be limited to no more than 4 of the first 14 evaluable patients and no more than 11 of the 37 evaluable patients. Patients who receive SRT to other sites as well as to brain metastases will not be counted towards this allotment.

Accrual is anticipated to be about 1 patient every 1-2 months over a period of about 4.5 years.

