### 13.3 Statistical Analysis of Primary Objective

We will employ a Simon two-stage design to assess for treatment futility by examining the rate of improved disease control at 24 weeks following completion of SRT. Therefore, 14 patients will be evaluated for the primary endpoint (ie, improved disease control) at 24 weeks. If at least 2 successes are observed, we will continue to recruit a total of 42 evaluable patients. If fewer than 2 successes are observed, then the study will close to further accrual. If 8 or more success are observed in the total population of 42 evaluable patients, further investigation of this treatment regimen will be considered warranted.

At the end of the first stage, all primary and secondary endpoints will be summarized and shared with the Data Safety and Monitoring Committee (DSMC). If the study goes into the second stage of accrual, this will be the interim analysis. If early termination of the study is recommended, this will be the final analysis.

The rate of improved disease control will be reported with a point estimate and 95% confidence interval. Analysis of the primary objective will include all efficacy-evaluable patients; however, a subset analysis of efficacy-evaluable patients who only receive SRT to brain metastases will also be performed.

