#### 13.5.2 Efficacy-Evaluable Population

Patients will be evaluable for analysis of the primary endpoint if they meet all of the following criteria:

- Received at least 50% of the prescribed SRT
- Received at least one dose of PD-1 or PD-L1 inhibiting therapy after SRT
- Had baseline and at least one subsequent response assessment to measure the SRT-treated tumor **and** the non-SRT-treated tumor following the last dose of SRT as follows:
  - Patients with documented unequivocal progression of disease prior to the 24-week time point will be evaluable.
  - Patients who do **not** have documented unequivocal progression of disease prior to the 24-week time point **and have not** had an objective response assessment at the 24-week time point will not be evaluable for efficacy and will be replaced.

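### On the plan's own 10% rate, 46 enrolled gives 41.4 expected evaluable patients, not 42, and the plan does not say whether replacement may exceed 46

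*Combined protocol and SAP*

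**What the plan says.** Section 13.2 sets the target: "the study will require a sample size of 42 evaluable patients to have 80% power at 5% level of significance". It then allows for losses: "We anticipate that 10% of enrolled patients may be inevaluable; therefore, up to 46 patients are required to ensure" an adequate evaluable number. The next sentence adds a replacement rule: "Patients who are not evaluable for efficacy as defined in Section [13.5.2](#) will be replaced".

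Section 13.5.2 repeats that rule for patients with neither documented progression before week 24 nor a 24-week assessment; they "will not be evaluable for efficacy and will be replaced".

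Section 13.3 recruits to an evaluable count and defines success only for that count: "If 8 or more success are observed in the total population of 42 evaluable patients", further investigation is considered warranted.

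No section says whether replacement may take enrolment above 46.

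**The concern.** Two things do not fit.

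- **The inflation.** The 10% is stated as a fraction of those enrolled. The target should therefore be divided by 0.90. The stated 46 is one short of the result, so the planned enrolment does not reach the planned evaluable number even in expectation, although it is offered as ensuring it.
- **The ceiling.** An upper limit of 46 and an obligation to replace every inevaluable patient can both be met only while at most four patients are inevaluable (46 - 42 = 4). The fifth forces a choice that the plan does not make.

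At stake is which number ends accrual. If the ceiling governs, the trial may finish with fewer than 42 evaluable patients. The cut-off of 8 is not defined for such totals, and power is below the stated 80%. If replacement governs, the stated maximum enrolment is wrong.

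**Working it through.** **Inputs.** Target of 42 evaluable, 10% of enrolled inevaluable, enrolment up to 46, null rate 10%, promising rate 25%, 5% level, 80% power (all Section 13.2). Stage 1: 14 patients, continue with at least 2 successes. Final: 8 or more of 42 (Section 13.3).

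**1. The base figure of 42.** Exact two-stage calculation, with success probability p:

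P(declare success) = sum over x = 2 to 14 of P(Bin(14, p) = x) x P(Bin(28, p) >= 8 - x).

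At p = 0.10 this is 0.0464, and at p = 0.25 it is 0.8042. So 42 evaluable patients with these rules do meet a one-sided 5% level and 80% power.

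**2. The enrolment figure of 46.**

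- 42 x 1.10 = 46.2, which rounds to 46. This reproduces the stated number, but takes 10% of the evaluable patients rather than of the enrolled. Rounding 46.7 down would also give 46. The plan does not show its derivation.
- With 10% of enrolled inevaluable: 42 / (1 - 0.10) = 46.67, so 47.
- Check: 46 x 0.90 = 41.4; 47 x 0.90 = 42.3.

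**3. Ceiling against replacement.** 46 - 5 = 41 evaluable. Five of 46 is 10.9%, close to the planned rate. Replacing the fifth patient needs a 47th enrolment.

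**4. Chance of a shortfall if enrolment is fixed.** This assumes independent patients with a 10% chance of being inevaluable, no replacement beyond the fixed number, and a trial that passes stage 1. P(at least 42 evaluable) = P(Bin(n, 0.90) >= 42):

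| Enrolled | Expected evaluable | P(at least 42) |
|---|---|---|
| 46 | 41.4 | 50.7% |
| 47 | 42.3 | 67.1% |
| 48 | 43.2 | 80.0% |
| 49 | 44.1 | 88.8% |
| 50 | 45.0 | 94.2% |

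At 46 the chance of fewer than 42 is 49.3%. It is sensitive to the true inevaluable rate: 7.9% at 5%, 30.6% at 8%, 66.1% at 12% and 84.0% at 15%.

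**5. Cost of a shortfall.** Same formula, keeping 2 of 14 and the cut-off of 8, with the second stage cut to the total minus 14:

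| Evaluable | Power at 25% | Type I error at 10% |
|---|---|---|
| 42 | 80.4% | 4.6% |
| 41 | 78.9% | 4.2% |
| 40 | 77.2% | 3.7% |

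At 39 and 38 evaluable, power is 75.3% and 73.2%, but those exact counts have probability 8.8% and 4.8%. Weighting power by Bin(46, 0.90), with counts above 42 treated as 42, gives 78.5%.

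**The case against.** A reader might infer that the trial will miss its target about half the time. The documents do not support that. Replacement is stated in 13.2 and again in 13.5.2, and 13.3 ties recruitment to 42 evaluable patients. Nothing says that accrual stops at 46 with fewer than 42. Read together, these sections suggest that 42 would be reached and that 46 is a planning figure.

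Even under a hard cap, the shortfall matters only if the trial passes stage 1. That has probability 0.415 at a 10% success rate and 0.899 at 25%. If evaluability is independent of outcome, the chance of continuing and then falling short is 0.415 x 0.493 = 20% or 0.899 x 0.493 = 44%.

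It can also be said that the error is one patient (2.1% of 47), that the 10% is itself a round guess (at 8%, 46 x 0.92 = 42.3), and that 47 under a hard cap would still miss 42 about 33% of the time.

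All of this stands, and it makes the point minor. It does not remove it. The plan's own 10% does not lead to its own 42, *ensure* is not justified for 46 or for 47 taken as a fixed maximum, and the text leaves open which of ceiling and replacement governs.

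**Conclusion.** Wrong as written, but minor. On the inputs in 13.2 the enrolment figure should be 47, and 46 is one short. Separately, the maximum of 46 cannot hold together with replacement to 42 evaluable once five or more patients are inevaluable, and this needs to be resolved in the text.

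The shortfall risk of about 49% is conditional on a hard cap at 46, a trial that passes stage 1, and independent inevaluability at exactly 10%. Under those conditions the average loss of power is about 2 points (80.4% to 78.5%), and type I error does not rise. If replacement continues to 42, no power is lost and only the stated maximum is wrong. The calculations do not put the two-stage design itself in doubt: 42 patients with the stated rules meet the stated error rates.

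**What to change.** In Section 13.2, replace the sentence giving the maximum of 46 with one saying that about 47 patients (42/0.90) are expected to be needed. Add that replacement of inevaluable patients continues until 42 are evaluable, even if enrolment goes beyond that number. The second part matters more, because 47 as a fixed ceiling would reach 42 only 67.1% of the time.

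If 46 has to remain a ceiling, say that it overrides replacement, drop the word *ensure*, and state that about 41 evaluable patients are expected with power of about 78-79%. Section 13.3 should then say how the cut-off of 8 applies to fewer than 42 patients.

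Cost: one corrected sentence and about one more expected patient; or, with the ceiling kept, a stated power 1 to 2 points lower and a short addition to 13.3.
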